Aim 3: To assess the association between time toxicity scores and survey-based measures (e.g. QOL), we will calculate individual time toxicity scores over the data collection period and fit linear regression models of the form $M_e = \gamma_0 + \gamma_1 S + \gamma_2 M_b + \gamma_3 X + \epsilon$ where M_e and M_b are survey measures taken at the beginning and end of the data collection period, S is the time toxicity score, and X is a set of individual-level covariates for adjustment. Separate models will be fit for each survey instrument used (e.g., FACT-G for QOL, HADS for depression and anxiety). Initially, we will fit unadjusted versions of these models (with $\gamma_3 = 0$) to assess whether the time toxicity score is associated with the final survey measurement, controlling only for the baseline survey measurement. Then, we will fit covariate-adjusted models to see whether associations between the time toxicity score and survey measures remain after controlling for individual characteristics. In exploratory analyses, we will investigate whether the associations between the time

SOCIAL PROTOCOL (HRP-580)

PROTOCOL TITLE: Time toxicity of cancer: the time demands of cancer-related activities and their impact on well-being and quality of life

VERSION DATE: 02/27/2024

toxicity score and survey measures are modified by individual-level covariates by including $S \times X$ interaction terms in the above regression model. Finally, we will investigate whether specific subtype scores are more strongly associated with survey measures by replacing the overall time toxicity score in the above model by the four subtype scores.

17.4 Data Integrity: Data integrity and completeness will be monitored on an ongoing basis by the study coordinator and statistician, using both the reporting tools provided by REDCap and the study/data management dashboard associated with the app.

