13.0 Withdrawal of Participants

- 13.1 Withdrawal Circumstances: No participant will be withdrawn from the study against their will. Participants will only be withdrawn from the study if they ask to withdraw, become too ill or die prior to completing the study. If participants become too ill, they will not be withdrawn from the study until they have given their voluntary consent for study withdrawal.
- 13.2 Withdrawal Procedures: If a participant chooses to withdraw at any point, their decisions will be respected without repercussions. Data collected until the point of withdrawal will be used unless the participant specifies otherwise.
- 13.3 Termination Procedures: Participants will not be terminated from the study for any reason.

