14.0 Risks to Participants

- 14.1 Foreseeable Risks: This study has few risks. We identified the following 2 possible risks to subjects:

Risk to confidentiality: Inadvertent breaches of confidentiality by investigators or their staff are unlikely but may occur. Identifying information will be kept private and all identifiers will be removed prior to any data being given to researchers. The records will be identified only with a unique ID number on an encrypted database. Data transfer will only occur with de-identified data with encrypted transfer of all information containing protected health information between participants and study databases.

The Dynamica app records information about daily activities, including relevant locations such as home and work. These data are potentially highly sensitive, and hence there is a non-trivial risk of loss of confidentiality and privacy if the data are accessed inappropriately. We have put multiple safeguards in place to ensure data security, including strict guidelines about which study team members have access to

SOCIAL PROTOCOL (HRP-580)

PROTOCOL TITLE: Time toxicity of cancer: the time demands of cancer-related activities and their impact on well-being and quality of life

VERSION DATE: 02/27/2024

which data, and how the data are to be used. In addition, the Dynamica app empowers users by providing an interface to review and edit all data collected (e.g., change start/end times, modify activity types and trip modes, etc.). Further, users are always free to turn off the app during time periods where they would prefer not to be tracked.

Discomfort while interacting with the app or answering survey questions: There is a possibility that some participants may feel uncomfortable interacting with the app or when answering survey questions which may remind them of their cancer diagnosis. They will be reminded that they can skip any questions or discontinue at any time.

The data from these studies will not be used to direct patient care. Therefore, participation in this study will have no influence on the care the patient receives nor will it influence treatment decisions.

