17.0 Statistical Considerations

17.1 Data Analysis Plan:

SOCIAL PROTOCOL (HRP-580)

PROTOCOL TITLE: Time toxicity of cancer: the time demands of cancer-related activities and their impact on well-being and quality of life

VERSION DATE: 02/27/2024

Aim 1: For the time use component, we will focus on characterizing the distributions of summary measures of time use by activity and trip type. Similar to our previous work,[19] we will compute, for each activity/trip type, the number of minutes per day spent on that activity, the number of separate episodes, and the number of days per week on which that activity occurs. For common activities and trip types (home, work, driving), means and variances of these measures generally provide useful summaries of how individuals engage in these activities. For less common activities such as cancer care-related activities, total number of episodes, total time spent, and the mean/variance of episode duration may be more meaningful summary measures.

Aim 2: *Qualitative analysis component.* Some individual circumstances (for example, competing time demands, level of support, flexibility of employers) that either buffer against or aggravate the burden cannot be easily ascertained from our app- and survey-based measurements. Therefore, we will examine free-text responses to open-ended survey questions. All entries will be transcribed. We will examine themes and consistencies. Two coders will read the entries and apply the constant comparative method to analyze and code data. As themes are identified, coders will return to the transcripts to reread and recode excerpts, thus ensuring that themes are grounded in data. A computer-assisted qualitative data analysis system (NVivo) will be used to enhance these analyses.

Aim 3: *Generating a time toxicity score.* Using the Dynamica app-based spatiotemporal data collected in Aim 1, we will calculate time-based measures for each individual that characterize the degree of burden and disruption to daily life associated with receiving treatments for cancer. We propose to quantify four subtypes of time toxicity: episodic toxicity, travel toxicity, opportunity toxicity, and scheduling toxicity. Each of these subtypes is described by a different set of time-based measures. **Table 2** lists the four subtypes and describes the time-based measures that we will calculate to characterize each subtype.

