Aim 1: Our planned sample size of 80 participants strikes a balance between feasibility and statistical precision and power to estimate the quantities of interest. We will recruit 40 participants with breast and ovarian cancer undergoing treatment at each of the two sites over a two-year period. We do not anticipate any difficulties obtaining this sample size. The UMN and UAB sites combined treat approximately 80 patients with newly diagnosed ovarian cancer, 100 with recurrent ovarian cancer, and 300 patients with metastatic breast cancer annually; therefore we will need to recruit <10% of eligible patients into this study over two years.

For descriptive statistics of individual-level measures (e.g., mean number of minutes per week spent on cancer care related activities) on the entire sample, we will be able to estimate means of continuous measures with a margin of error of ± 0.22 standard deviations. For example, if the average number of minutes per week spent on cancer care in the sample was 250 with a standard deviation of 80, then the 95%

SOCIAL PROTOCOL (HRP-580)

PROTOCOL TITLE: Time toxicity of cancer: the time demands of cancer-related activities and their impact on well-being and quality of life

VERSION DATE: 02/27/2024

confidence interval for the mean number of minutes would be (232, 268). For comparing means of individual-level measures between two equal-sized subgroups (e.g., those with breast and ovarian cancer), our sample size yields 80% power to detect a difference of 0.64 standard deviations, equivalent to approximately 50 minutes using the same standard deviation as above. Our power to detect associations and differences for day-level measures will be higher since we will have ~20-28 (correlated) observations per person.

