Aim 2: Though we have a limited number of individuals in our study, we will have sufficient power to detect associations between daily time use and self-reported well-being as we will have 28 days of observations for each participant. To estimate power, we conducted a simulation study to estimate the effect size of a binary daily time use measure (e.g., whether or not a medical appointment occurred on a given day) and continuous well-being. We generated probabilities of having a medical appointment from a Beta(2,4) distribution and well-being measures from a linear mixed model calibrated to have a mean of 3, a (Normal) residual standard deviation of 1.5 units, and within-person correlation of approximately 0.4. With 28 days of observations on N=80 participants, we estimate that we will have approximately 90% power to detect a difference of 0.25 units between days within different characteristics. An effect of this magnitude (approximately 5% of the range of the 1-6 well-being scale) seems plausible and is at or below a threshold likely to be clinically meaningful. Power to detect associations between continuous time use measures (e.g., number of hours spent on medical appointments) and well-being will be higher than for the binary measures.

Aim 3: The main target of inference in this aim is the association between the time toxicity score and survey measures at 28 days. With our planned sample size of n=80, we will have >80% power to detect a 0.4 standard deviation effect on survey measures associated with a 1 SD difference in the time toxicity score. Previous studies from our team among this target population identified a standard deviation of 17 points for the FACT-G QOL instrument,[44] hence a 0.4 SD effect would correspond to a difference of 6.8 points. This effect size corresponds to a "medium" effect on the FACT-G as suggested by a meta-analysis of studies using FACT-G as an outcome [45] and is in line with the effects demonstrated by supportive activities for cancer treatment such as muscle relaxation [46] and associations with co-occurring conditions such as skeletal morbidities.[47] Further, it has been previously shown that effect sizes of 0.35-0.5 are expected to be clinically relevant for QOL measures.[48]

17.3 Statistical Analysis:

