Aim 1: These per-activity summary measures will be used as outcomes in generalized linear regression models to quantify differences between relevant subgroups (e.g., those caring for dependents vs. not, those experiencing higher vs.

SOCIAL PROTOCOL (HRP-580)

PROTOCOL TITLE: Time toxicity of cancer: the time demands of cancer-related activities and their impact on well-being and quality of life

VERSION DATE: 02/27/2024

lower treatment burden) adjusting for individual demographic and clinical characteristics. For example, we will be able to compute covariate-adjusted differences in the total number of episodes and minutes spent on various cancer care-related activities between patients with and without dependents, which will provide insight into how family structure affects the time burden of care. Random effects models will be used to quantify associations between factors that vary day to day within individuals and time use outcomes, e.g., to understand whether completing a cancer care-related task on a given day affects the number of hours spent working or engaged in leisure activities. In addition, we will apply techniques developed by [name] and colleagues [49] to describe day-level activity patterns via sequence alignment (see **Figure 1**). These techniques will allow us to identify clusters of days with similar activity sequences, and quantify how individual participants' characteristics determine their likelihood of experiencing these different day archetypes.

Aim 2: Relating cancer-related time use measures to self-reported well-being.

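### Aim 1 models raw totals of cancer-care episodes and minutes with no adjustment for observed time, so a subgroup contrast in totals is biased if observed days differ by subgroup and care on unobserved days goes unrecorded

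*Combined protocol and SAP*

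**What the plan says.** Sections 3.1 and 17.1 (Aim 1) list three measures for every activity and trip type: minutes per day, number of separate episodes, and days per week on which the activity occurs. The episode count has no stated divisor. For less common activities, including cancer care, Section 17.1 then adds that "total number of episodes, total time spent, and the mean/variance of episode duration may be more meaningful summary measures".

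Section 17.3 (Aim 1) uses the per-activity measures as outcomes in generalized linear models, "adjusting for individual demographic and clinical characteristics". Its worked example is "covariate-adjusted differences in the total number of episodes and minutes spent on various cancer care-related activities", comparing patients with and without dependents. Neither section gives Aim 1 an offset, a divisor for observed time or a rule for missing days. The remark in Section 17.1 about incomplete data concerns the Aim 3 score.

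Other sections imply that observed time will vary:

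- Section 17.2 (Aim 1) says that power for day-level measures will be higher "since we will have ~20-28 (correlated) observations per person". Section 17.2 (Aim 2) instead reasons "as we will have 28 days of observations for each participant".
- Section 14.1: "users are always free to turn off the app during time periods where they would prefer not to be tracked".
- Section 13.2: "Data collected until the point of withdrawal will be used unless the participant specifies otherwise".

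**The concern.** A total over the collection period is a care rate multiplied by the time over which care could be recorded. If one person contributes 20 days and another 28, their totals differ at equal weekly burden. Demographic and clinical covariates need not absorb that difference.

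The plan's own example compares people with and without dependents. If those groups differ in how many days they keep the app running, or in early withdrawal, part of any difference in totals reflects observation rather than burden. A larger sample does not shrink a bias of this kind.

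**Working it through.** **The plan's figures.** Section 17.2 (Aim 1) uses N = 80 and an illustration: "if the average number of minutes per week spent on cancer care in the sample was 250 with a standard deviation of 80".

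- Margin: 1.96/√80 = 0.219 SD (plan: 0.22).
- Interval: 250 ± 1.96 × 80/√80 = 250 ± 17.5, or 232.5 to 267.5 (plan: 232 to 268).
- Power for 0.64 SD with 40 per group: 0.807 by t-test (plan: 80%). 0.64 × 80 = 51.2 minutes (plan: about 50).

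All reproduce. They concern a weekly measure and are not in dispute.

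**Size of the shift.** Let r be the weekly care rate, d the sensor-tracked days out of 28, and s the share of care on untracked days that is still recorded. With the same care rate on all days:

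- Expected total = (r/7) × [d + s(28 − d)].
- For two groups with equal r and s and a gap of g in mean tracked days, the difference in totals is (r/7)(1 − s)g. As a fraction of the 28-day total 4r, this is (1 − s)g/28.
- s = 0: 1/28 = 3.6% per day of gap. For one person, 20 days against 28 gives 20/28 = 0.714, a total 29% lower.
- s = 0.5: 1.8% per day of gap. s = 1, or g = 0: no shift.

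At 250 minutes per week and s = 0, each day of gap moves the contrast by 250/28 = 8.9 minutes per week. The 95% margin for 40 against 40 is 1.96 × SD × √(2/40):

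| SD (min/week) | Margin (min/week) | Gap giving a shift of that size |
|---|---|---|
| 80 (plan's illustration) | 35.1 | 3.9 days |
| 125 (assumed) | 54.8 | 6.1 days |
| 250 (assumed) | 109.6 | 12.3 days, wider than the 20–28 range |

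**Simulation with s = 0.** Set-up: 40 against 40, 10,000 runs, equal true burden, gamma-distributed minutes with mean 250, tracked days uniform within ±2 of 24 ± gap/2, two-sided 5% t-test on totals. The 5% test is a yardstick; the plan sets none for this contrast. Rejection rates:

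| SD | Gap 0 | 1 day | 2 days | 4 days |
|---|---|---|---|---|
| 80 | 5.6% | 8.5% | 20.7% | 62.7% |
| 125 | 4.8% | 6.4% | 11.8% | 31.2% |
| 250 | 4.8% | 5.6% | 6.1% | 10.8% |

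For episode counts (assumed mean 1–2 per week, between-person CV 0.32–1.0), the rates are 6–12% at 2 days and 10–31% at 4 days.

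**Choice of denominator.** If all recorded care is divided by sensor-tracked days alone, the expected value is (r/7)[1 + s(28 − d)/d], which depends on d whenever s > 0. If numerator and denominator cover the same days, it is r/7 for any d and s. At SD 80 and a 4-day gap:

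| Untracked-day care recorded | Raw totals reject | All care ÷ sensor-tracked days | Same days in both |
|---|---|---|---|
| None | 62% | 5% | near 5% |
| Half | about 17% | about 24% | near 5% |
| All | 5% | 63% | near 5% |

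A log-link gamma model with a log(days) offset (1,000 runs, s = 0, 4-day gap) rejected 7.1%, 5.8% and 7.0% at SD 80, 125 and 250, against 61.4%, 31.6% and 12.6% without the offset. The offset version runs slightly above nominal.

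**The case against.** **Care can be recorded on sensor-off days.** Section 5.2 gives an end-of-day survey asking about cancer-related activities not otherwise reported and the time they took, and lets participants edit and add detail to episodes. Section 14.1 repeats that they can review and edit what the app collected. This stands. It shrinks the shift, and it rules out the simple remedy of dividing everything by sensor-tracked days. It does not help after withdrawal or on days with neither sensor data nor survey.

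**The large rejection rates are extreme.** The 62–63% figure needs the smallest SD, no recovery of untracked care, and a 4-day gap in which one group tracks 20–24 days and the other 24–28. No section supports a gap of any size. This also stands.

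**The 20–28 figure is loose.** It appears in a remark about day-level power and counts observations; reading it as days with data is an interpretation. A missed survey is not necessarily an untracked day, and the Aim 2 power argument assumes 28. Switching off and partial data after withdrawal still make unequal observation likely.

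**Totals are not the only outcome, and Aim 1 is descriptive.** Minutes per day and days per week sit beside the totals, and the wording on totals is tentative. But Section 17.3 names totals as a modelled contrast, and a biased difference misleads whether or not it is tested.

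**Other safeguards exist.** Section 4.0 replaces people who never install and use the app, Section 12.5 pays for completing the 28 days, and Section 17.4 monitors completeness. These reduce the risk; none enters the model.

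A reader might infer that Aim 1 as a whole is invalid, or that its contrasts will be wrong. The documents do not support that: rates counted over the same observed days and mean episode duration do not scale with observed time in this way, and no section gives observed days by subgroup.

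**Conclusion.** The point holds in conditional form. As written, the Aim 1 totals combine burden with observed time, and no adjustment is stated. A subgroup contrast in totals is biased if observed days differ by subgroup and care on unobserved days is not recorded. At a constant care rate with none of that care recorded, the bias is about 3.6% of the 28-day total per day of gap, or about 9 minutes per week on the plan's illustrative mean. It falls in proportion to the share of care recovered through the survey or edits, and is zero with no gap.

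The gap, the recovered share and the real SD are all unknown, so the rejection rates illustrate sensitivity and do not predict this study's results. The stated power and precision figures are unaffected.

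**What to change.** In Sections 17.1 and 17.3 (Aim 1):

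1. Define an observed day as one with sensor data or a completed end-of-day survey.
2. Count cancer-care episodes and minutes only on observed days.
3. Model them per observed day, or with a log link and offset log(observed days), so that numerator and denominator cover the same days. Use the same denominator for the per-day and per-week measures.
4. Report observed days by subgroup.
5. Show the raw totals as a sensitivity analysis.

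The cost is a definition, one model term and one table. It needs no new data and adds nothing for participants. The limit is that it assumes the same care rate on unobserved as on observed days, so it does not correct informative loss of tracking. The denominator should not be sensor-tracked days alone while survey-reported care stays in the numerator, because that can itself create a spurious contrast.

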1.0 Objectives

1.0 Purpose: Our overall objectives are to 1) measure, describe, and quantify sources of cancer-related time toxicity among individuals treated for cancer, and their effect on QOL; and 2) create time toxicity scores which can be used in future studies to identify opportunities to minimize time toxicity. Our specific aims are:

Aim 1: Measure and describe components of objective time use associated with cancer-related healthcare interactions via a mobile health application.

Aim 2: Characterize associations between measures of cancer-related time use and self-reported well-being, and explore the role of context in modifying these associations.

Aim 3: Create a time toxicity summary score based on measures of cancer-related time use and assess its association with psychosocial outcomes.

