We will compute an individual's score for each time toxicity subtype by calculating an average of z-scores for each of the time-based measures associated with that subtype. This z-score averaging approach is commonly applied in a wide variety of domains to generate a single summary metric from observations taken on different subscales.[40-43] For example, if there are five time-based measures associated with a subtype (for example, those associated with Episodic Toxicity listed in Table 2), then we will first compute a z-score for each measure by subtracting its average and dividing by its standard deviation across all individuals. All features will be transformed so that higher values correspond to higher time burdens. The summary score for the subtype will be computed by averaging the five z-scores, then converting the resulting average into a population percentile from a standard Normal random variable expressed as a number out of 100. For example, if the

SOCIAL PROTOCOL (HRP-580)

PROTOCOL TITLE: Time toxicity of cancer: the time demands of cancer-related activities and their impact on well-being and quality of life

VERSION DATE: 02/27/2024

average of the summary feature z-scores associated with travel toxicity is 1.05, then the travel toxicity score will be $P(Z<1.05) \times 100 = 85$, while a z-score average of -0.42 would lead to a travel toxicity score of $P(Z<-0.42) \times 100 = 34$.

Table 2. Time use subtypes and measures

Toxicity Subtype	Spatiotemporal Measures
1. Episodic Toxicity Toxicity associated with activities directly related to care.	
 • Number of days with a medical appointment per week • Number of days receiving treatment per week • Hours per week spent in medical appointments • Hours per week spent receiving treatment
2. Travel / Wait Time Toxicity Toxicity associated with traveling to/from and waiting for medical appointments	
 • Number of trips to/from appointments per week • Hours per week spent traveling to/from appointments • Hours per week spent waiting for appointments • Average distance traveled to/from medical appointments

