3. Opportunity Toxicity Toxicity associated with the opportunity cost of time spent on cancer treatment-related medical activities	
 • Time spent on medical appointments as a fraction of time spent at home, on work, leisure, education, childcare, caregiving, and household • Proximity of medical appointment/treatment locations to individual points of interest (home, work, etc.) • Variation of schedule between days with and without a medical appointment
4. Scheduling / Administrative Toxicity Toxicity associated with paperwork, scheduling appointments, dealing with bills and insurance, arrangement to accommodate cancer-related activities	
 • Number of different locations associated with cancer care • Number of appointments per week • Hours per week spent on scheduling and administrative cancer work • Weekly variation in the duration of medical appointments and calls • Variation in time between medical activities

The overall time toxicity score will be a weighted average of the four subtype scores $S_1, S_2, S_3, S_4: T = w_1S_1 + w_2S_2 + w_3S_3 + w_4S_4$ where the weights are constrained to sum to one. We will consider several versions of the time toxicity score defined by the relative weights of the various subtypes. The simplest time toxicity score is one where each subtype is assigned equal weight, and therefore the overall score is a simple average of the population percentiles across the four subtypes. For example, if an individual has subtype scores of 55, 75, 60, and 90, then their time toxicity score will be $(55 + 75 + 60 + 90)/4 = 70$, which suggests that their time toxicity burden is higher than approximately 70% of the population. In some scenarios, it may be appropriate to pre-specify non-equal weights for the different

SOCIAL PROTOCOL (HRP-580)

PROTOCOL TITLE: Time toxicity of cancer: the time demands of cancer-related activities and their impact on well-being and quality of life

VERSION DATE: 02/27/2024

subtypes; for example, personalized time toxicity scores could be generated based on individuals' prior weightings of each subtype, which, for example, might give opportunity toxicity more weight than travel toxicity.

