In addition to pre-specified (equal or unequal) weights, we will also use our daily burden and well-being measures to derive data-driven versions of the time toxicity score. Let M_{ij} denote the daily well-being measure of person i on day j . We will fit the model $M_{ij} = \beta_0 + \beta_2 X_{ij} + \theta_1 S_{1ij} + \theta_2 S_{2ij} + \theta_3 S_{3ij} + \theta_4 S_{4ij} + \epsilon_{ij}$ where X_{ij} represents a set of individual, and day-level covariates, and $S_{1ij}, S_{2ij}, S_{3ij}, S_{4ij}$ are the subtype scores computed for person i on day j . The coefficients $\theta_1, \theta_2, \theta_3, \theta_4$ represent the relative weightings of the subtypes that best predict the mean of M after adjusting for covariates. These coefficients will be standardized to yield weights using the formula $w_k = \theta_k / \sum \theta_k$.

Our proposed approach to deriving time toxicity scores was developed with a view towards how this score may be used in clinical practice going forward. First, computation of the score relies only on time use summary metrics, which could be collected in a variety of ways. While the collection of these metrics is made substantially easier by the app, the time toxicity score could also be applied to time use summary metrics obtained via traditional diary-based recall methods. Second, the four component scores provide easy to understand insights into which types of time use are driving the overall score, and may allow clinicians and patients to better identify interventions (e.g., increased use of telehealth) that could reduce time toxicity. Lastly, the score can be easily adapted to different populations (by re-weighting subtype scores), applied with incomplete data (by using either imputed or complete-case data to compute subtype scores), and computed across a range of time periods.

17.2 Power Analysis:

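### The time toxicity score is called a population percentile, but the stated algorithm does not produce one; a score of 70 will usually sit well above the 70th percentile

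*Combined protocol and SAP*

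**What the plan says.** The Aim 3 part of section 17.1 builds the score in three steps.

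1. Each time-use measure is turned into a z-score by "subtracting its average and dividing by its standard deviation across all individuals". Measures are transformed only so that higher means more burden.
2. Within each of the four subtypes the z-scores are averaged. The subtype score comes from "converting the resulting average into a population percentile from a standard Normal random variable expressed as a number out of 100". The plan's examples are a mean z of 1.05 giving 85 and a mean z of -0.42 giving 34.
3. The overall score T is a weighted average of the four subtype scores. With equal weights, "the overall score is a simple average of the population percentiles across the four subtypes". The example has subtype scores of 55, 75, 60 and 90 and a total of 70, "which suggests that their time toxicity burden is higher than approximately 70% of the population".

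No section re-standardises the mean z-score, ranks T, or transforms the measures to Normality.

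Section 3.1 makes the score the Aim 3 primary outcome. Section 1.0 aims to "create time toxicity scores which can be used in future studies to identify opportunities to minimize time toxicity", and section 17.1 says the approach was "developed with a view towards how this score may be used in clinical practice going forward".

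**The concern.** The standard Normal distribution function returns a percentile only for a quantity that is itself standard Normal. A mean of several z-scores is not, unless the measures are perfectly correlated. Averaging four such scores moves the total further from a percentile scale, because people are rarely high on every subtype at once and totals bunch around the middle. Right-skewed measures, which are plausible for hours and visit counts, add a third departure.

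The reference group is a separate problem. The means and standard deviations come from the study participants (80 planned, at two sites), so the score can at best describe position within that sample.

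What is at stake is interpretation. A later user told that 70 means worse than about 70% of patients would usually understate how unusual that patient's burden is. The concern is limited to scores in the upper range.

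**Working it through.** **Inputs from the documents.** The algorithm and worked examples are in section 17.1. Table 2 lists 4, 4, 3 and 5 measures for the four subtypes. The text speaks of five Episodic measures while Table 2 lists four; using five moves the results below by no more than about 0.2 points. The planned n is 80 (section 17.2).

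**Inputs assumed.** The documents give no correlations and no distribution shapes. All of these are assumptions and are shown as ranges.

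**Reproducing the plan's figures.** 100 × Φ(1.05) = 85.3; 100 × Φ(-0.42) = 33.7; (55 + 75 + 60 + 90)/4 = 70. The arithmetic is right.

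**Step 1: subtype score, closed form.** For k measures with common correlation ρ, the mean z-score has

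SD = sqrt((1 + (k - 1)ρ)/k).

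For Normal measures its true percentile is Φ(mean z / SD). For the plan's travel example, mean z = 1.05 and k = 4:

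| ρ | SD | True percentile of the score labelled 85 |
|---|---|---|
| 0.2 | sqrt(1.6/4) = 0.632 | 95.2 |
| 0.4 | sqrt(2.2/4) = 0.742 | 92.2 |
| 0.6 | sqrt(2.8/4) = 0.837 | 89.5 |
| 0.9 | sqrt(3.7/4) = 0.962 | 86.3 |

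**Step 2: averaging alone.** Suppose each subtype score were an exact percentile, so that step 1 causes no error. In simulation, T = 70 then lies at about percentile 88, 83, 78, 75 and 71 for between-subtype correlations of 0.1, 0.3, 0.5, 0.7 and 0.9. Averaging breaks the percentile reading by itself.

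**Step 3: the full algorithm.** This was simulated with 400,000 draws, equal weights, 4/4/3/5 measures, and one general factor plus four subtype factors. Entries are P(T < 70) in percent. For the log-normal columns the correlations are on the log scale.

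| Correlation within / between subtypes | Normal | Log-normal, sigma 0.5 | Log-normal, sigma 0.8 |
|---|---|---|---|
| 0.2 / 0.1 | 91.6 | 92.9 | 94.5 |
| 0.4 / 0.2 | 86.4 | 89.1 | 91.4 |
| 0.6 / 0.3 | 82.7 | 86.7 | 89.6 |
| 0.7 / 0.5 | 77.8 | 82.7 | 86.1 |
| 0.6 / 0.6 | 75.5 | 80.3 | 83.9 |
| 0.7 / 0.7 | 73.8 | 79.3 | 83.2 |
| 0.8 / 0.8 | 72.3 | 78.4 | 82.4 |
| 0.9 / 0.9 | 71.1 | 77.7 | 82.1 |

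The choice of skew matters. From all correlations 0.9 to 0.2/0.1, a milder shape (gamma, shape 2) gives 76.5 to 92.6 and a stronger one (log-normal, sigma 1.0) gives 85.0 to 95.6.

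**Step 4: in the study itself.** If 70 were a true percentile, about 0.30 × 80 = 24 participants would score 70 or more. In 2,000 simulated samples of 80, z-scored within sample, the mean number for Normal measures was 6.6 (0.2/0.1), 13.7 (0.6/0.3), 19.6 (0.6/0.6), 21.1 (0.7/0.7) and 23.2 (0.9/0.9). It was 5.8 to 18.3 for sigma 0.5 and 4.9 to 15.2 for sigma 0.8.

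**The case against.** **Nothing inferential depends on the label.** This is true. Section 17.3 uses the score as a regressor, the Aim 3 power in section 17.2 is stated per 1 SD of the score, and section 14.1 says the data will not direct care. The transform is also stated openly and works as a 0–100 index. This limits the harm to interpretation but does not make the label correct.

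**The sentence is a hedged illustration of the simplest of several score versions.** The hedging covers a gap of one or two points, not ten or more. It does not extend to the two other places in section 17.1 that use the percentile term without qualification.

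**Many Table 2 measures track the same visits, so correlations should be high and 70 roughly right.** This is the strongest point, and it stands in part. With Normal measures and all correlations at 0.8 to 0.9, the plan's reading is fair, and the 0.2/0.1 end of the range is unlikely for the visit-count measures. Three things limit it:

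- Distance, proximity and variation measures need not follow visit volume. With visit-volume measures correlated 0.7 to 0.9 and the others only weakly related, T = 70 falls at about percentile 75 to 88.
- The plan's own example spreads its subtype scores over 35 points. Among simulated people with T near 70 (Normal measures), a spread that wide occurs in about 0.7% at 0.8/0.8, but in 48 to 63% for settings from 0.2/0.1 to 0.7/0.5, where 70 is percentile 78 to 92.
- With log-normal skew (sigma 0.5 to 0.8) the label is off by about 8 to 12 points even at 0.9/0.9.

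**One skewed shape for all 16 measures is crude.** Agreed. The skewed columns are illustrative. The closed-form result in step 1 needs no skew.

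**Conclusion.** The concern holds. That the algorithm does not yield a percentile follows from algebra whenever the measures are less than perfectly correlated. The size of the gap depends on correlations and shapes that the documents do not give. Over the assumed settings, a score of 70 is percentile 71.1 to 91.6 for Normal measures and 77.7 to 94.5 for log-normal measures with sigma 0.5 to 0.8. The plan's reading is acceptable only for near-Normal measures with correlations of about 0.8 or more throughout.

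This should be fixed, because the wrong definition is attached to a primary outcome meant for reuse. It does not invalidate any planned test, estimate or power figure.

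**What to change.** In section 17.1, delete the closing interpretation of the 70 example and remove the percentile wording from the subtype conversion and from the equal-weight definition. Describe S1–S4 and T as 0–100 indices relative to the study sample. This changes three sentences and no analysis.

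If a percentile is wanted for reporting, add the empirical rank of each person-level subtype score and of T as a separate quantity, and name the reference sample. Ranking T as written keeps the participants' order and takes a line of code.

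Keep T as written as the regressor. If a ranked T were used instead, say so, since it is a slightly different variable. Ranking the subtypes and then T gives a correlation with T as written of 0.984–1.000 (Normal), 0.975–0.985 (sigma 0.5) and 0.954–0.964 (sigma 0.8). At 0.954, a 0.40 SD slope becomes 0.40 × 0.954 = 0.38. Power in a simple regression with n = 80 (two-sided 5%, no baseline adjustment) then goes from about 97% to 95%.

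Do not rank the day-level scores in the data-driven weighting model, which "are the subtype scores computed for person i on day j". The Aim 2 power section says "We generated probabilities of having a medical appointment from a Beta(2,4) distribution", which has mean 2/6. About 67% of person-days would then have no appointment, and appointment-based measures would be heavily tied.
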